- In the *forward number span* task, participants see a series of numbers (from 3-7 digits long) and have to enter the numbers in the order they appeared. In the *backward number span* task, participants again see a series of numbers (from 2-6 digits long) and have to enter the numbers in reverse order.
- In the *spatial n-back* task, participants see 4 squares that change color. When the same square changes color twice in a row, they have to click a button on the screen.

7. During the same 14 days, participants will also wear an accelerometer watch (MotionLogger Actigraph) on their non-dominant wrist during all waking and sleeping hours to objectively assess sleep and activity/sedentary behavior. They will be instructed in its use, including removal of the wristwatch for any water-based activities (e.g., showering, bathing, swimming, etc.).

8. On Day 15 (i.e., the day immediately after completion of the 14-day ambulatory assessments), participants will return to the laboratory for the experimental visit. They will return the accelerometer at this visit.

Daily Saliva Collection (Days 3-6)

1. Participants will be asked to provide saliva samples for 4 consecutive days, beginning on Day 3 of the ambulatory assessments (described above) and continuing until Day 6. These samples will be tested for stress hormones (e.g., cortisol) and indices of mitochondrial function (e.g., cell-free mitochondrial DNA). The home saliva collection kit contains collection instructions (see attached document "Saliva Collection Instructions"), all collection materials, and a saliva collection worksheet (see attached document "Saliva Collection Worksheet") and is provided in a small portable cooler for ease of transportation and storage. All samples are coded and do not contain personal identifiable information.
2. Participants will collect their saliva 4 times per day (once upon awakening and before getting out of bed, once 30 minutes after getting out of bed, once at lunchtime, and once in the evening). Participants will record the date and time of each collected saliva sample. They will collect a total of 16 saliva samples over the 4-day sampling timeframe.
3. To collect saliva, participants will use a salivette, which includes a cotton swab that they will put in their mouth for 2 minutes. After 2 minutes, they will place the cotton swab back in the salivette tube.

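### The two morning saliva samples are timed from different events (awakening and rising), so the interval between them is 30 minutes plus an unlimited time awake in bed

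*Combined protocol and SAP*

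**What the plan says.** Section 6 (Procedures), under Daily Saliva Collection (Days 3-6), sets the schedule. Item 1 gives the days: "Participants will be asked to provide saliva samples for 4 consecutive days, beginning on Day 3". Item 2 gives the frequency, "Participants will collect their saliva 4 times per day", and the total, "They will collect a total of 16 saliva samples over the 4-day sampling timeframe". The first two samples are taken "once upon awakening and before getting out of bed, once 30 minutes after getting out of bed"; the other two are at lunchtime and in the evening.

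Item 2 also says: "Participants will record the date and time of each collected saliva sample". It does not ask for a separate time of awakening or of rising. Item 1 gives cortisol and cell-free mitochondrial DNA as example analytes.

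The ambulatory assessment in the same section adds two possible checks on wake time: a wrist accelerometer worn day and night over the same 14 days, and a morning survey that includes sleep questions. Neither is linked to the saliva timing.

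The analysis text in section 10 (Data) plans mainly multilevel models and multilevel structural equation models. It names no term for saliva sampling time.

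**The concern.** Salivary measures taken soon after waking may depend on time since awakening. If so, the second sample should fall at a known and reasonably constant time after that event. Here the rule itself distinguishes awakening from rising, then uses one for the first sample and the other for the second. A participant who follows it exactly still supplies a second sample at an uncontrolled time since awakening.

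Two consequences are possible. If time awake in bed varies haphazardly, it adds noise to anything built on the second sample. If it differs on average between adults with MDD and healthy adults, or changes from day to day with sleep, mood or anticipated stress, the timing difference could be read as a group or daily-stress effect. Section 5 describes MDD in terms of depressed mood, anhedonia and functional impairment, so a group difference in time to rise is plausible. The documents do not report one.

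The protocol gives no reason for timing the second sample from rising. Elsewhere it does explain deliberate variation: section 6 justifies the unstandardized gap of about 3-6 months between testing cycles.

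**Working it through.** **Inputs.** Four samples per day, four days per cycle and a stated total of 16 (section 6, Daily Saliva Collection); two testing cycles (section 6, opening description). No document gives a value for time awake in bed, so those values below are assumptions.

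**The plan's own figure.** 4 samples/day × 4 days = 16 samples per cycle, which matches. The count is not in question.

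**The interval.** Let W be the time of awakening and L the minutes from awakening to rising.

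- Sample 1, taken at awakening: W.
- Sample 2, taken 30 minutes after rising: W + L + 30.
- Interval = (W + L + 30) − W = 30 + L minutes.

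| Assumed L (min) | Sample 2, minutes after awakening |
|---|---|
| 0 | 30 |
| 10 | 40 |
| 15 | 45 |
| 30 | 60 |
| 60 | 90 |

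**Group or day differences.** The 30 minutes is common to everyone, so a mean difference of d minutes in L becomes a mean difference of exactly d minutes in the interval. With assumed means of 15 minutes in one group and 5 in the other, the intervals are 45 and 35 minutes, a difference of 10. The same holds for one person on two mornings with different L.

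**With a common anchor.** If sample 2 were due at W + 30, the scheduled interval would be (W + 30) − W = 30 minutes for every L. A difference in L would then no longer shift the schedule. The total stays at 16.

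**What the recorded times can do.** If sample 1 is taken promptly, its recorded time approximates W, and the difference between the two recorded times gives 30 + L directly. If sample 1 is late by e minutes, the recorded difference is 30 + L − e and understates time since awakening by e. Each participant can contribute up to 4 mornings × 2 cycles = 8 mornings. Within-person variation in L can therefore help to estimate the effect of timing separately from group in a multilevel model.

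**The case against.** The strongest reply is that no declared outcome is affected. Aims 1-3 in section 5 concern cytokine production, mitochondrial redox balance, endothelial function and cognition. They do not name cortisol, and no section defines a change from sample 1 to sample 2. Four samples a day could serve a daily average or a diurnal slope. This stands, and it limits the importance of the point. A reader might infer that a planned comparison of the morning cortisol response is biased, but the plan declares no such comparison.

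Second, the group difference in L is conjecture. This also stands. A reader might go further and turn an assumed gap into a percentage error in cortisol. That needs a gap and a rate of change per minute, and the documents supply neither. Nor should one set a delayed MDD group against controls sampled at exactly 30 minutes: controls also have some time in bed, and only the difference in L carries over to the comparison.

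Third, sample times are recorded, and the accelerometer and sleep questions offer a rough check. A reader might infer that the recorded times cannot help, or that any adjustment is inseparable from group. With up to 8 mornings per person, that is too strong. What remains is that adjustment is partial. It relies on self-recorded times, prompt collection of sample 1 and an assumed shape for the time course, and no such adjustment is written down.

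Last, the Saliva Collection Instructions and Worksheet are not reproduced and may define the timing differently or capture wake time. If they do, they and item 2 need to be brought into agreement.

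**Conclusion.** The point holds as a minor, avoidable weakness in a stated rule. That the scheduled interval is 30 + L minutes, with no limit on L, follows from the wording of item 2 and needs no assumption. The resulting timing variation in the morning saliva measures follows if participants differ, or vary from day to day, in how long they stay in bed after waking.

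Bias in a group or daily-stress comparison is only a possibility. It requires L to differ by group or to vary with the day's stress, and the analyte to be changing over that period. The documents are silent on its size and direction. They do not support a claim that the stated aims are compromised. The change is worth making because it costs little, removes a source of noise and possible bias at the design stage, and leaves less to statistical adjustment.

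**What to change.** 1. In section 6, Daily Saliva Collection, item 2, time the second sample at 30 minutes after awakening, whether or not the participant has got up.
2. Check the Saliva Collection Instructions and Worksheet and align them with that wording. A field for wake time on the Worksheet, if there is none, would make the check direct.
3. In section 10, state that models of the morning saliva measures will include actual time since awakening, calculated from the recorded sample times. This is useful even after re-timing, because participants will not always collect on schedule.

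**Cost.** A small amendment to the protocol and the participant materials. The number of samples and the kit do not change. The documents do not say whether collection has started. If it has, the data will contain two timing rules: flag the version for each participant and cycle, and rely on item 3 to put the two on a common time scale.

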7. STUDY POPULATION AND RECRUITMENT

Describe who and how many subjects will be invited to participate. Include age, gender and other pertinent information.

- 18 – 55 yrs

- Males and females
 - 60 non-depressed healthy adults will have no evidence of current or lifetime history of major psychiatric illness, assessed by the MINI and self-report
 - 60 unmedicated adults with MDD will meet the DSM-5 criteria for MDD, assessed by the MINI and self-report; participants with co-morbid anxiety, stress, and trauma-related disorders will be included if MDD is the primary diagnosis
 - 30 selective serotonin reuptake inhibitor (SSRI)-treated (current monotherapy) adults with MDD will meet the DSM-5 criteria for MDD, assessed by the MINI and self-report; participants with co-morbid anxiety, stress, and trauma-related disorders will be included if MDD is the primary diagnosis

Subjects will be recruited from the University of Delaware and surrounding local communities. We use recruiting methods that will reach a large percent of the general population. We advertise for subjects, and interested persons contact us. We post recruitment flyers in various campus (e.g., student union, classroom building bulletin boards, dormitory bulletin boards, campus eateries, etc.) and community (e.g., coffee shops, bookstores, local businesses, etc) locations. We will obtain permission to provide recruitment flyers to local medical and wellness practices (family physicians, mental healthcare providers/specialists, etc.) and other locations specifically targeted to recruit patients with depression (e.g., Center for Counseling & Student Development). Additionally, the text from the fliers may be utilized in “word of mouth” recruiting if the opportunity presents itself. Recruitment may also occur via online social media resources (e.g., Instagram, Twitter, Google, Craig’s List, NextDoor, Facebook, ResearchMatch.com, etc.), as well as in campus newsletters and local newspapers/mailings.

Attach all recruitment fliers, letters, or other recruitment materials to be used. If verbal recruitment will be used, please attach a script.

Advertisements

- Study Information.svcMDD.20240118
- CHS ad
- gen.recruit.ad.bookmark
- gen.recruit.ad.buisinesscard
- recruit general.unMDD_1
- recruit general.unMDD_2
- CPP Recruitment EDDM Postcard
- svcMDD.research match.20240701

Describe what exclusionary criteria, if any will be applied.

The exclusion criteria are applied to all groups. We will not enroll non-English-speaking individuals. This protocol involves the use of numerous questionnaires, including a detailed neuropsychiatric interview with the investigators. In addition, participants need to understand English to follow instructions and comply with procedures conducted during the screening and experimental visits.

Subjects will be excluded at the discretion of PI/collaborating psychiatrist/examining clinician or for any of the following reasons:

- Psychiatric illness aside from MDD (e.g., bipolar disorder, schizophrenia, eating disorders), assessed by the MINI and self-report
- Active current suicidal ideation with intent or a specific plan, assessed by the Columbia-Suicide Severity Rating Scale
- Active current suicidal behavior with a preparatory attempt, assessed by the Columbia-Suicide

Severity Rating Scale

- Active substance dependence, assessed by the MINI
- Current or recent (within 8 wks) use of medications that could conceivably alter neural-cardiovascular-immunological function [including (but not limited to) antihypertensives and HMG-CoA reductase inhibitors] or psychoactive or psychopharmacological drugs aside from SSRIs [including (but not limited to) antidepressants, antipsychotics, benzodiazepines, mood stabilizers, sedatives/hypnotics, dopaminergic agents, stimulants, buspirone, and triptans]
- Changes or alterations in medication status (starting a new, additional, or different medication or changing the dose of a current medication)
- Unstable or diagnosed chronic clinical disease, including cardiovascular, metabolic, renal, hepatic, autonomic, autoimmune, or dermatological disease (e.g., hypertension, heart disease, diabetes, hyperlipidemia, psoriasis)
- Body mass index <18.5 or >35 kg/m²
- Tobacco or nicotine use, including vaping and electronic cigarettes
- Pregnancy (including a positive urine pregnancy test) or breast-feeding
- Lack of access to a device with internet connectivity
- Known allergies to pharmacological agents/drugs

Describe what (if any) conditions will result in PI termination of subject participation.

Subjects will be terminated from participation if it is believed that such participation endangers their welfare or for an inability to comply with study procedures.

8. RISKS AND BENEFITS

List all potential physical, psychological, social, financial or legal risks to subjects (risks listed here should be included on the consent form).

Neuropsychiatric Interview and Depressive Symptom Severity/Suicidality Assessments

- General: There is risk that adults with MDD will experience clinical worsening.

Mitigation: We have robust standard operating procedures in place to ensure the safety of participants. In no case will a participant be denied necessary medical or psychiatric treatment for reasons related to study participation. No patients with MDD who are currently treated with antidepressant pharmacotherapy will be asked or allowed to discontinue to participate. We have multiple screening and crisis protocols in place to ensure patient safety and compliance with study procedures. Psychiatric mental health advanced practice registered nurses and a licensed clinical psychologist will provide psychiatric clinical oversight for the management of adults with MDD. Our crisis intervention plan allows for rapid referral, including immediate referral for acute psychiatric issues (described below and in accompanying documents). This crisis protocol can be triggered at any time and at the discretion of the research team. If a participant has worsening of MDD but no immediate safety concern, we will recommend that the patient seek psychiatric consultation. If participants have questions regarding clinical care, they will be referred to a mental healthcare provider. If a participant does not have a mental healthcare provider, the investigators will help them to identify local resources. All participants will be given materials on local resources for psychiatric care and suicide hotline information. To ensure safe participation, subjects will be asked to identify an emergency contact and provide contact information so that the study team may contact these individuals in case of an emergency.

- MINI/PHQ-9/PROMIS: For the purposes of this study, we use these tests to identify potential subjects who have MDD (or not) and to identify for exclusion those who have psychiatric illness

other than depression. These interviews have been extensively validated in multiple clinical populations and are based on standard diagnostic criteria. Answering questions related to mental health and past experiences may be stressful and uncomfortable for participants. Some subjects may be disturbed if the test recommends their inclusion as an adult with depression.

Mitigation: Subjects are reminded that they may decline to answer the questions and leave the study at any time. We remind them that the test is not intended to be a diagnosis or healthcare recommendation but is used as a tool to identify people who may have particular experiences or forms of psychological distress useful for the purposes of this study. Research interviews will be interrupted if subjects become too distressed or object to answering questions. If, in the judgment of the study team or the PI, the patient has worsened to a degree that further participation would put the patient at risk, the subject will be discontinued from the study and encouraged to seek appropriate clinical care. Also, at any point during the study, any subject meeting DSM-5 criteria for any exclusionary psychiatric diagnoses (detailed above) will be discontinued from the study and encouraged to seek appropriate medical care. All participants are highly encouraged to seek follow-up with a healthcare provider and the study team will assist with identification of and communication with treating providers as needed. The investigators also will provide the subjects with a detailed explanation of the neural-cardiovascular physiology of depression-related cardiovascular disease. Furthermore, the investigators will provide subjects with their screening data so that they may forward this information to a health care provider.

- C-SSRS: Answering questions related to mental health and past experiences may be stressful and uncomfortable for participants.

Mitigation: All suicidal behaviors are taken seriously, and it is important to assess the risk of suicide carefully when working with individuals with MDD. Many people may admit to fleeting thoughts of death or briefly wishing for death; these thoughts need to be considered in context of the subject's overall history, along with a consideration of other risk factors for suicide. Due to these reasons, as part of informed consent process, subjects will be asked to identify an emergency contact person and provide their contact information so that the study team may contact these individuals in case of an emergency. We have extensive experience in working with individuals with elevated risk of suicide and maintaining the safety of individual subjects. We have developed strict safety guidelines for this study, including detailed crisis protocols that can be implemented at any time for acute psychiatric issues. This safety plan was developed in consultation with our collaborating psychiatric mental health advanced practice registered nurses, who will provide general psychiatric clinical support for this project. This crisis protocol will be triggered if participants express 1) active current suicidal ideation with intent or a specific plan, 2) active current suicidal behavior with a preparatory attempt, or 3) at the discretion of the research team. The presence of suicidal ideation without intent will not trigger any additional assessments, as this is considered low acute risk. *For immediate assistance during an acute crisis in the laboratory, 911 will be called.*

Interviews/Surveys and Clinical Evaluations

- Initial Determination of Eligibility: We use this pre-screening interview to grossly determine whether a potential subject is a possible candidate for the study. The initial interview gathers minimally invasive personal healthcare information. We have used similar interviews in the past with potential participants.

Mitigation: Only trained study personnel administer this interview. The participants may decline to answer questions or participate. All data are collected using secure online platforms approved by the University of Delaware. We keep the completed forms confidential and secure.

Only approved staff may access the results.

- Medical Screening and Health History: There are no known risks with obtaining height, weight, waist circumference, heart rate, or blood pressure or collecting medical health history information. Subjects may be uncomfortable giving medical information or being measured.

Mitigation: The clinical evaluation and medical health history are performed by trained staff. The participants may decline to answer questions or participate in measurements. The researchers conduct screenings professionally and privately.

- Ambulatory Assessments of Daily Stress Processes and Cognitive Function: These surveys help us to interpret the physiological data we record during the experiment. Subjects may feel shy or disturbed by the questions. Reporting on stressful events may result in some sadness or anger or remind the participant of previous stressful experiences. Completing the “brain games” may cause some frustration.

Mitigation: Participants may choose not to answer the questions and decline to be in the study. We do not use the tools to decide a recommendation for healthcare. We keep the data resulting from the completed assessments confidential and secure. Only approved staff may access the results.

- Cognitive Function Assessments: These tests help us to interpret the physiological data we record during the experiment. Completing the “brain games” may cause some frustration. Subjects may feel shy or uncomfortable by the tasks.

Mitigation: They may choose not to answer the questions and decline to be in the study. We do not use the tools to decide a recommendation for healthcare. We keep the completed forms confidential and secure. Only approved staff may access the results.

- Surveys (Physical Activity Questionnaire, Life Events Checklist, etc.): These surveys help us learn of a subject’s experiences that are useful for the purposes of this study. The surveys help us to interpret the physiological data we record during the experiments. Subjects may feel shy or disturbed by the questions. Subjects may be uncomfortable giving information about their lives. Reporting on stressful events may result in some sadness or anger or remind the participant of previous stressful experiences.

Mitigation: They may choose not to answer the questions and decline to be in the study. We do not use the tools to decide a recommendation for healthcare. We keep the completed forms confidential and secure. Only approved staff may access the results.

Screening/Experimental Procedures

- Intradermal Microdialysis: Intradermal microdialysis commonly causes some pain and bruising similar to that experienced during venipuncture. There is usually no pain after the probe is in place. The participant may experience mild pain while the researchers remove probe. Minor bleeding may occur. As with routine venipuncture, a participant who is nervous about needles could have increased heart rate and blood pressure, become lightheaded or nauseated, or could faint.

Mitigation: Only trained personnel perform this technique. Ice numbs the skin, and the small needle reduces pain during insertion. Subjects are asked about allergy to iodine and, for those who are, alcohol is used instead. The researchers stop any bleeding following probe insertion by applying mild pressure to the site with sterile gauze. In the unlikely event that the individual

has an allergic reaction, the researchers stop microdialysis immediately. If the reaction becomes severe, the researchers seek emergency medical assistance. As with venipuncture or any event that breaks the skin, infection is possible, but proper aseptic technique and sterile solutions/supplies keep this risk minimal. Additionally, no participants in any of the PI's experiments have reported infection (over 1,500 probes have been placed by [name]). The researchers place a sterile bandage on the site after the experiment. Although rare, if the membrane should break in half during removal, they remove the remaining half by gently pulling the attached tubing. This presents no additional risk to the participant.

- Microdialysis Perfusates/Pharmacological Agents: Lactated Ringer's solution flows through the microdialysis probes. An allergic reaction to this physiological saline solution is highly unlikely. All substances (LNAME, Tempol, mitoTempol, sodium nitroprusside) added to the lactated Ringer's perfusing the microdialysis probes have been used previously clinically and/or in research in humans. Microdialysis delivers small amounts of the substances to a nickel-sized area of the skin. The small quantities used and the extremely localized administration during microdialysis does not produce systemic effects. To the researchers' knowledge, there are no reports of long or short-term side effects of these substances administered through microdialysis. The chance of adverse reactions to these substances is extremely small given the minute amount delivered to a very small area of skin, the lack of adverse reactions to similar amounts delivered via microdialysis in many other studies, and lack of adverse effects in human cell cultures. There is a slight chance of allergic reaction to these substances that could produce redness, itching, rash, and/or swelling. A severe reaction (anaphylactic shock) could also cause fever, difficulty in breathing, changes in pulse, convulsions, and/or loss of consciousness/lightheadedness. Although unlikely, in the case of a severe reaction to the perfusate, the researchers call 911.

General Note: Intradermal Microdialysis is a safe and effective method to locally deliver pharmacological agents directly to the cutaneous vasculature. This technique is widely used to administer small quantities of investigational agents to the cutaneous vasculature, and the PI has extensive experience with this technique. Pharmacological agents delivered using microdialysis do not affect the systemic circulation. All investigational agents have been previously used in humans. It is common in microdialysis studies to obtain research grade formulations of these agents because of their purity.

Mitigation: The perfusate is sterile. The researchers prepare the perfusate in their laboratory using sterile techniques and supplies commonly used for this purpose in research laboratories. The Ringer's solution is sterile as purchased. They add other solutions aseptically through 0.2 micron Gelman Sterile Acrodisc syringe filters. They mix the perfusate for same-day use and discard excess perfusate after the experiment. We use only USP grade when available or the purest form of the pharmacological perfusates possible (>98% purity). Although unlikely, in the case of a severe reaction to the perfusate, the researchers call 911.

- Flow-Mediated Dilation of the Brachial Artery: Placing the probe on the arm's skin may cause temporary minor redness. The temporary redness from the probe is unlikely to have lasting ill effects. The inflated cuffs may cause the participant's arms and feet to feel numb or tingly, and the skin's color to change slightly. The cuffs could cause mild bruising. The gel may feel cool or cold on the skin.

Mitigation: Only trained personnel perform this technique. Measures will be taken efficiently. The cuffs inflate for a minimal amount of time. The investigator can manually deflate the cuff at any time during the procedure, if necessary. The gel is the same as that used with medical ultrasound tests. A bad reaction to the gel is highly unlikely.

- Pulse Wave Analysis and Pulse Wave Velocity: The proposed assessments of arterial stiffness are non-invasive. The inflated cuffs may cause the participant's arm and/or feet to feel numb or tingly.

Mitigation: Only trained personnel perform this technique. Measures will be taken efficiently. The cuffs inflate for a minimal amount of time. The investigator can manually deflate the cuff at any time during the procedure, if necessary.

- Intravenous Catheterization: Insertion of an intravenous catheter can cause anxiety (with increased heart rate and blood pressure), mild pain, swelling, nausea, lightheadedness, fainting, or bleeding. There is a slight chance of infection or small blood clot.

Mitigation: Subjects may decline the procedure. A competent and trained research nurse performs the technique using standard procedures and techniques that minimize the chance of infection. Sterile supplies are used. Participants will be supine for the procedure. Subjects will only be subjected to a maximum of two attempts.

- Venous Endothelial Cell Biopsy: The risks of venous endothelial cell biopsy are similar to those of intravenous catheterization, including some pain, redness, swelling, or bruising. Rare side effects include a slightly greater risk of blood clots and infection than that of an intravenous catheter due to increased manipulation of the blood vessel. There is a low likelihood that the vein is damaged.

Mitigation: Subjects may decline the procedure. A competent and trained research nurse performs the technique using standard procedures and techniques that minimize the chance of infection. Sterile supplies are used. Participants will be supine for the procedure.

- Venipuncture: Blood draws can cause anxiety (with increased heart rate and blood pressure), mild pain, swelling, nausea, lightheadedness, fainting, or bleeding. There is a slight chance of infection or small blood clot.

Mitigation: Subjects may decline the procedure. A competent and trained investigator or research nurse performs blood draws using standard venipuncture-procedure and techniques that minimize the chance of infection. Sterile supplies are used. Participants may recline for the procedure. Subjects will only be subjected to a maximum of two attempts per arm by one person.

- Blood Pressure (automated): The automated methods use a cuff that inflates on the upper arm. The cuff slowly deflates. The inflated cuff may make the arm feel tingly and numb, and the cuff may temporarily bruise the arm. Efficient and competent measurement technique minimizes the duration of cuff inflation.

Mitigation: Efficient and competent measurement technique minimizes the duration of automated cuff inflation. This includes, but is not limited to, using the appropriate cuff size, correctly positioning the cuff, reminding the participant to minimize movement during measurements, etc. The cuffs inflate for a minimal amount of time. The investigator can manually deflate the cuff at any time during the procedure, if necessary.

- Accelerometry: There are no known risks with wearing an accelerometer. Minor skin irritation may occur.

Mitigation: Subjects may decline the procedure.

- Confidentiality: There is a risk of loss of confidentiality when completing study assessments and procedures.

Mitigation: All data are stored on password-protected computers in a locked room. Only authorized members of the lab have access to these files. REDCap (Research Electronic Data Capture) is a secure online platform for building and managing basic and clinical research protocols and features built-in data monitoring, back-up, and security (including electronic signatures and form/record locking). Qualtrics and Metricwire are secure survey administration applications designed to support data capture for research studies. Data are deleted from cloud servers within 24 hours. The data files are downloaded and stored on an external password-protected hard-drive.

In your opinion, are risks listed above minimal* or more than minimal? If more than minimal, please justify why risks are reasonable in relation to anticipated direct or future benefits.

The risks listed above present more than minimal risk of harm to subjects. Although the risks are more than minimal, they are low. Data from this study will help to understand the mechanisms of vascular dysfunction in young-to-middle aged adults with MDD.

*(*Minimal risk means the probability and magnitude of harm or discomfort anticipated in the research are not greater than those ordinarily encountered in daily life or during the performance of routine physical or psychological examinations or tests)*

What steps will be taken to minimize risks?

Strategies to minimize risks associated with specific techniques and procedures are described in detail in the preceding section.

- General Procedures: The research group's members are trained and competent in their duties. The group, led by [name], evaluates the effectiveness and safety of protocols and procedures in an ongoing fashion. They discuss the protocol with candidates, invite questions, and offer tours of the laboratory. Prior to medical screening, candidates read and sign informed consent forms detailing protocols, procedures, risks, sensations, compensation, etc. The researchers give candidates witnessed copies of the signed consent forms. Guided by the inclusion and exclusion criteria, the investigators and clinical staff screen subjects before participation to ensure that the subjects meet the study's requirements. After enrolling participants in the study, the researchers discuss and review the procedures and protocols with them generally and at each step throughout the project. They frequently remind participants of the option to withdraw from the study at any time. Restricting access to experiments, data, and coding to authorized personnel maintains confidentiality. Lists of emergency numbers remain by lab telephones. At least one cell phone is present at each experiment. A hospital and emergency medical services are within 6 miles of the lab. An AED hangs nearby in the hallway.
- Availability of Medical/Psychological Resources: We have developed strict safety guidelines for this study, including detailed crisis protocols that can be implemented at any time for acute psychiatric issues. Subjects will be free to contact the PI or study team regarding any concerns or emergency during the study. All participants will be given materials on local resources for psychiatric care and suicide hotline information. To ensure safe participation, subjects will be asked to identify an emergency contact person and provide their contact information, so that the study team may contact these individuals in case of an emergency.

- Stoppage Criteria: Although such events are extremely unlikely to occur, the investigators are prepared to immediately stop experiments and seek medical assistance if the subjects should experience the more serious reactions, such as signs and symptoms of an allergic reaction, anaphylactic shock, and fainting. In the case of a medical emergency, emergency services will be contacted. The investigators end the experiments if the subject's blood pressure is greater than 220/110 mmHg or less than 80/50 mmHg, if heart rate is >150 bpm or <40 bpm, or the presence of symptoms. The investigators will stop the experiments at any time should a subject wish it. Also, the investigators will exercise the discretion to end a subject's participation if the subject should engage in behavior that could jeopardize his/her own health and well-being or that of others.
- Previously Unknown Medical Conditions: It is possible that the investigators will discover a participant's previously unknown medical condition because of the screening. At the time of screening, the investigators inform subjects of any condition identified that might require further treatment and will suggest follow-up with a healthcare provider. The investigators make the results from laboratory studies available to the subject as soon as possible.

Describe any potential direct benefits to participants.

All study subjects will be informed that there may not be any potential benefit to them individually because of taking part in the study. All study subjects will receive (without cost) an extensive psychiatric and medical evaluation, which may be of potential benefit for the subjects. Participants may gain knowledge about the biological and psychological processes of depression, as well as the implications for cardiovascular disease risk, which they may find interesting and helpful in dealing with the illness. The subjects receive financial compensation. No other direct benefits result from study participation.

Describe any potential future benefits to this class of participants, others, or society.

Approximately 50% of adults in the US will manifest cardiovascular disease (CVD) during their lifetime, contributing substantially to the global burden of disease and disability. This health issue is pervasive and exacts emotional, physical, and financial costs. Cardiovascular disease is the leading cause of morbidity and mortality in modern societies. This risk appears to be further heightened in adults with MDD. The information to be gained is essential to the understanding increased CVD risk in adults with MDD. The results from this study will determine if the links between emotional responsiveness to daily stress and 1) proinflammatory cytokine production, 2) mitochondrial redox balance, and 3) vascular dysfunction are sensitized in adults with MDD. These data will provide information that could be valuable in designing interventions to promote mental and physical health in adults with and without MDD.

If there is a Data Monitoring Committee (DMC) in place for this project, please describe when and how often it meets.

No

